### 2.2.1 Secondary Outcomes

We specify the diagnosis and procedure codes used to measure the utilization of preventative care for children under 2 in Table 2.1. We will construct these outcomes using Medicaid claims data. We define receiving the share of recommended well-child visits as a binary indicator equal to one if a child has received at least the number of well-child visits in the first 2 years of life as recommended by the American Academy of Pediatrics. In the case of multiples we will consider binary outcomes to have occurred if all children from the index birth meet the criteria.

Table 2.1. Preventative Care Utilization Measures

Outcome	Outcome Definition	Code(s)
Well-child visits	Binary indicator equal to 1 if the child has received 9 well-child visits by 24 months	ICD-10: Z00.1; CPT: 99391, 99392
Lead screening	Received at least one lead screening by 24 months	ICD-10: Z13.88; CPT: 83655
Developmental screening	Received at least one developmental screening by 9 months	ICD-10: Z13.41, Z13.42; CPT: 96110
Dental visit	Received at least one dental visit by 12 months	NA
Fluoride treatments	Binary indicator equal to 1 if the child has received at least one fluoride treatment by 24 months iii	ICD-10: Z293; CPT: 99188

iii While our protocol paper specified this outcome as receiving at least four fluoride treatments, there are inconsistent guidelines regarding the recommended number of visits. Therefore, we have modified the definition of this outcome to be a binary variable indicating whether any fluoride treatments were received. See <https://www.uspreventiveservicestaskforce.org/uspstf/recommendation/dental-caries-in-children-from-birth-through-age-5-years-screening> for details on fluoride varnish recommendations.

### **2.3. Timing of study analyses**

We will complete analysis of the primary outcome and related secondary outcomes once all study births have occurred, and at least 24 months have elapsed following the study birth. We will add additional lags to account for the time it takes for administrative records to be complete, sent to the study team, and matched to existing analytic files. If we make additional changes to the analysis plan before starting the analysis, we will indicate those changes with a new version number and date. We plan to publish analyses of the primary outcome and related secondary outcomes first. A separate manuscript is planned to explore outcomes related to preventative health care utilization for children. We also plan to conduct follow-up analyses of similar outcomes as children age, including beyond the time when families would participate in NFP. Analytical plans for follow-up longitudinal analyses will be added as they are developed.

### **2.4. Attrition and Missing Outcome Data**

We will report on the following categories of mother-baby dyads for whom we may not be able to see outcomes related to child health, reporting on the sample of children tracked to 12 months and 24 months separately:

- a. *Mortality prior to 12 or 24 months of age:* We will use vital records to identify children born into the study who experience mortality prior to the age of 12 months.
- b. *Unmatched to Medicaid Eligibility through 12 or 24 months of age:* We will consider children who never match to Medicaid eligibility in any of their first 12 months of life or 13-24 months of life respectively.

We will report rates of missingness for each category listed here for the whole sample and by treatment arm in order to characterize missing outcome data and identify differential rates of missing outcome data across treatment arms in each of these categories.

### **2.5. Endogeneity of Data Sources and Sensitivity Analysis**

As discussed above, because child preventative health outcomes will be observed exclusively in Medicaid claims data, we will not observe these outcomes among children who are not enrolled in Medicaid. Because NFP may affect maintenance of Medicaid coverage through the child's first two years of life, child enrollment rates in Medicaid may differ between control and treatment groups.

We will conduct several analyses to determine whether rates of enrollment in Medicaid differ between treated and control groups. First, we will compare enrollment through the first year of life and the first two years of life across treatment and control groups. Even if we do not observe differences in Medicaid enrollment rates between the two groups, the type of children retaining coverage may be influenced by participation in NFP. Therefore, we will also test

whether there are differences in the characteristics of participants between control and treatment groups over the two time periods (12 months and 24 months). We will use a joint F-test to compare characteristics measured at baseline across these two groups using the list of baseline covariates specified in section B.1.

When conducting study analyses, we will report outcomes observed over the first year of life, where more children are likely to be enrolled in Medicaid as well as outcomes over the first 24 months of life. As specified in our study protocol in Section 2.12, we will report our primary outcome excluding data that comes from Medicaid to assess the robustness of our results to this potential source of endogeneity. If we observe significant differences in Medicaid enrollment across treatment and control groups in the second year of life, we may focus more on outcomes that can be measured within the first year of life.

## **2.6. Subgroups**

Our primary sub-group is described in the study protocol. Briefly, this subgroup is composed of women who report mental health challenges, are under 19 years of age, or have not completed high school/received a GED certificate by the time of enrollment.

In addition to the planned subgroup described above, we may also consider other potential sub-groups of particular importance for outcomes related to child health. In particular, we are interested in focusing on child outcomes where the first year of the child's life was completed prior to the start of the COVID-19 pandemic (defined here as March 23, 2020). We expect that the pandemic altered the way that the NFP program was implemented. In addition, it is likely that the pandemic substantially affected clinical practices and utilization of pediatric care.

## **2.7. Accounting for Multiple Hypothesis Testing**

We have planned for the analysis of several outcomes related to utilization of preventative care for children. To account for multiple related secondary outcomes in the domain of preventative care we will construct an index of preventative care-seeking, similar to the approach proposed by Kling, Liebman and Katz 2007. We will report the index in addition to other outcomes.

## **Nurse-Family Partnership Evaluation Analysis Plan Addendum 3: Alter Maternal Life Course**

*Note: This version of Addendum 3 reflects plans for study design as of January 15, 2021.*

The goal of this analysis plan addendum is to enumerate analysis specific to the outcome domain focused on birth spacing and family planning utilization.

### **3. Methods**

A full treatment of our empirical approach, primary study outcomes, planned subgroup analyses, and statistical power is given in sections 2.4-2.10 of McConnell et al. (2020). The following sections provide additional context and details on auxiliary analysis for the outcomes related to altering the maternal life course including birth spacing and family planning utilization.

#### **3.1. Defining the Sample for Analysis**

The sample will be restricted to women with a fetal death or index birth as defined in section A1 of the pre-analysis plan.

#### **3.2. Construction of Study Outcomes**

We outline the construction of study outcomes across two domains: outcomes related to birth spacing and outcomes related to the utilization of contraceptive methods.

##### **3.2.1. Construction of birth spacing outcomes**

Data will be obtained from vital statistics birth records. In the case of multiples, birth spacing will be measured as the time between the date of birth of the last child from the index pregnancy to the date of birth of the first child from the subsequent pregnancy. There may be cases where the subsequent birth is implausibly close to the index birth. Births that occur less than or equal to 90 days from the index birth will be assumed to be multiple gestation based on guidelines provided by the National Center for Health Statistics. Subsequent births that occur between 90 days and 21 weeks (147 days) after the index birth will be considered outliers and will be dropped from the analysis. We define birth outcomes of interest in Table 3.1.

Table 3.1. Birth spacing outcomes

Birth spacing outcomes	Follow-up
Inter-birth interval of < 21 months (primary outcome)	21 months
Inter-birth interval of < 24 months	24 months
Inter-birth interval of < 15 months	15 months

Inter-birth interval (continuous)	60 months
-----------------------------------	-----------

### 3.2.2. Construction of contraception outcomes

Table 3.2 summarizes outcomes related to the utilization of contraceptive methods. The primary data source used for the contraception outcomes will be Medicaid claims data. Medicaid claims capture contraceptive provision among Medicaid enrollees that takes place in the hospital before discharge (inpatient), during outpatient hospital visits, and during ambulatory clinical visits. We will rely primarily on Medicaid claims data because most postpartum contraceptive provision occurs after hospital discharge. However, we will also supplement Medicaid discharge data with hospital discharge data to capture any inpatient contraceptive provision that may be missing from Medicaid claims. Any family planning related counseling or service will include any diagnosis code, procedure code, CPT code, or HCPCS codes for contraceptive counseling, the intrauterine device, implant, injectable, contraceptive pill, patch, ring or diaphragm (See Table 3.3 below) and National Drug Codes for the contraceptive pill, patch, and ring identified by the Office of Population Affairs Contraceptive Care Measures. Receipt of a moderately effective method of contraception will include all of the above methods but will not include contraceptive counseling without provision of a contraceptive method. Immediate postpartum contraception will include diagnosis, procedure, CPT or HCPCS code for an intrauterine device or contraceptive implant.

Contraceptive counseling and/or contraceptive receipt within six weeks of hospital discharge will meet the criteria for the 6-week contraceptive outcomes. Contraceptive counseling and/or receipt within 12 months of the date of hospital discharge will meet the criteria for the 12-month contraceptive outcomes.

Table 3.2. Contraceptive outcomes

Variables	Follow-up
Any family planning related counseling or service	6 weeks
Received a highly or moderately effective method of contraception 	6 weeks
Immediate postpartum long-acting reversible contraception	6 weeks
Any family planning related counseling or service	12 months
Received a highly or moderately effective method of contraception 	12 months
Postpartum intrauterine device insertion	12 months
Time to first family planning counseling or service (months from pregnancy)	24 months

 CDC defines highly effective contraception to include implant, Immediate Post-Partum-Long-Acting Reversible Contraception, Long-Acting Reversible Contraception, or sterilization and moderately effective contraception to include patch, ring, diaphragm, injectables and contraceptive pills.

Time to first utilization of highly effective contraceptive methods (months from discharge)	24 months
---	-----------

In Table 3.3 we define codes used to identify specific contraceptive methods that will be used in analyses. Codes will be identified in both Medicaid claims and hospital discharge records.

Table 3.3. Codes used to identify contraception

Contraceptive method	Diagnosis codes	Procedure	CPT	HCPCS
Female sterilization	Z30.2	0U574ZZ, 0U578ZZ, 0UL74CZ, 0UL74DZ, 0UL74ZZ, 0UL78DZ, 0UL78ZZ	58565, 58600, 58605, 58611, 58615, 58670, 58671	A4264
Intrauterine device	Z30.430, Z30.014	0UH97HZ, 0UH98HZ, 0UHC7HZ, 0UHC8HZ, 0UH90HZ	58300	J7300, J7301, J7302, S4989, Q0090, S4981, J7297, J7298
Contraceptive implant	Z30.017, Z30.46	0JHDOHZ, 0JHD3HZ, 0JHFOHZ, 0JHF3HZ	11981	J7306, J7307
Contraceptive injectable	Z30.013, Z30.42	--	--	J1050
Contraceptive pills, patch, ring	Z30.011, Z30.41, Z30.016, Z30.45, Z30.015, Z30.44	--	--	S4993, J7304, J7303
Diaphragm	--	--	57170	A4266, A4261

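### The immediate postpartum LARC outcome is coded as any IUD or implant up to six weeks after discharge, so outpatient insertions are reported under an immediate postpartum label

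*SAP*

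**What the plan says.** Everything on this outcome stands in SAP Addendum 3, section 3.2.2, with Tables 3.2 and 3.3.

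- Label and follow-up: Table 3.2 lists "Immediate postpartum long-acting reversible contraception" with a follow-up of 6 weeks.
- Definition: "Immediate postpartum contraception will include diagnosis, procedure, CPT or HCPCS code for an intrauterine device or contraceptive implant". This names methods and code systems. It gives no care setting, encounter or date.
- Window: "Contraceptive counseling and/or contraceptive receipt within six weeks of hospital discharge will meet the criteria for the 6-week contraceptive outcomes".
- Settings covered: Medicaid claims are described as capturing provision that "takes place in the hospital before discharge (inpatient), during outpatient hospital visits, and during ambulatory clinical visits". Hospital discharge data are added to catch inpatient provision that the claims miss.
- Search: for the methods in Table 3.3, "Codes will be identified in both Medicaid claims and hospital discharge records".

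Section 3.5 says that the six-week contraception outcomes will receive more emphasis if the programme (NFP) appears to affect Medicaid enrollment or the kind of woman who enrolls.

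**The concern.** The natural reading of immediate postpartum LARC is placement during the delivery stay. The coding rule does not require that. A device placed at a clinic weeks after discharge counts the same as one placed before the mother goes home.

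The two kinds of event reach NFP by different routes. In-hospital placement depends on prenatal planning and on what the delivery hospital offers. Later placement depends on attending an outpatient visit. The SAP treats postpartum visit attendance as an outcome in its own right (Addendum 1, Secondary Outcomes), and Addendum 4, Table 7 gives an increase as its desired direction. An effect that ran only through that visit would appear in the results as an effect on immediate postpartum LARC.

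**Working it through.** The plan attaches no rate, effect size or power figure to this outcome, so there is no stated figure to reproduce. The check is to apply the written rule.

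**Step 1: what scores as an event.** The window ends 6 × 7 = 42 days after discharge.

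| Event | IUD or implant code? | Searched source? | Within 42 days of discharge? | Score |
|---|---|---|---|---|
| Implant placed before delivery discharge | yes | yes (inpatient claim or discharge record) | yes, on the evident intent | 1 |
| Implant placed at a clinic at the end of week 5 (day 5 × 7 = 35) | yes | yes (ambulatory claim) | yes, 35 ≤ 42 | 1 |
| Implant placed at a clinic on day 50 | yes | yes | no, 50 > 42 | 0 |

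The first two rows score alike. The variable is therefore any IUD or implant by six weeks after discharge.

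**Step 2: does a restriction stand elsewhere?** None was found in either document. The data source does not supply one. The encounter data in protocol section 4.7.1 include outpatient surgery, emergency department and imaging records as well as inpatient records. The SAP does write delivery-anchored conditions where it wants them. In Addendum 1, NICU admission needs a claim on the delivery day and on the next day, and the hospital mental health outcomes leave out inpatient claims on the delivery day. Such a condition is therefore feasible with these data, and it is absent here.

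**Step 3: what the estimate then measures.** Let I = 1 for insertion before discharge. Let P = 1 for a first insertion after discharge and by day 42. The coded outcome is Y = I + P, so the treatment-control difference splits as

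ΔY = ΔI + ΔP.

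- If only outpatient insertion rises, by d: ΔI = 0, ΔP = d, so ΔY = d. The full effect carries the immediate postpartum label.
- If placement shifts from clinic to delivery stay, by d: ΔI = d, ΔP = −d, so ΔY = 0. The shift is invisible in this row.

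**Step 4: can the share be sized?** The share of events that are post-discharge insertions is o / (i + o), where i and o are the in-hospital and post-discharge rates. The documents give neither. With purely assumed rates:

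- i = 5%, o = 1%: 1/6 = 17%
- i = 5%, o = 5%: 5/10 = 50%
- i = 2%, o = 10%: 10/12 = 83%

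The answer is set by the assumption, so no share is claimed.

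**The case against.** The best defence is that Table 3.2 shows the six-week follow-up openly and neither document defines immediate as before discharge. On that view the variable is clear and only its name is loose. Renaming the row would settle the matter, whereas redefining it now could be a post-hoc change: Addendum 4 (February 2025) describes the trial manuscripts, family planning among them, as published or forthcoming. The SAP also leaves part of its method to the published study protocol, which is not among the documents reviewed, so a restriction stated there cannot be excluded. The row is one of eight in Table 3.2. The primary outcome of Addendum 3 is an inter-birth interval under 21 months, and this row is absent from Addendum 4, Table 6.

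Most of that stands. It limits the weight of the point and shapes the remedy. It does not remove the mismatch between the label and the rule.

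A reader might also infer more than the text supports:

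- *That the window opens at discharge and so excludes in-hospital insertion.* Section 3.2.2 lists inpatient provision among the settings captured and adds discharge data to find more of it. In-hospital provision is plainly meant to count.
- *That footnote 4 to Table 3.2 makes immediate postpartum LARC and LARC exclusive categories.* Its list reads "CDC defines highly effective contraception to include implant, Immediate Post-Partum-Long-Acting Reversible Contraception, Long-Acting Reversible Contraception, or sterilization". It names implants apart from LARC, although section 3.2.2 counts implants in the LARC row. The items overlap, and the footnote belongs to other rows.
- *That most events in this row must be outpatient insertions.* The SAP says that "most postpartum contraceptive provision occurs after hospital discharge", but that covers all methods, pills and injectables included. It does not say where IUDs and implants are placed.

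**Conclusion.** The point holds as a mismatch between label and rule. The outcome as written measures any IUD or implant by six weeks after discharge, and an NFP effect on outpatient insertion would be reported as immediate postpartum. This rests on the SAP text as it stands and on taking immediate postpartum to mean the delivery stay, which is the ordinary reading but is not defined in the documents.

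The consequence is modest. It concerns the interpretation of one non-primary outcome. It affects no sample size or power figure, and the variable is a valid measure under an accurate name. The extra emphasis on six-week outcomes in section 3.5 is conditional, but it is a reason to settle the name before results are interpreted.

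**What to change.** 1. Keep the pre-specified variable and change its name in Table 3.2 to *IUD or implant within 6 weeks of discharge*.
2. Add a separate row, *immediate postpartum LARC*, counting IUD or implant codes dated from delivery admission to delivery discharge, taken from Medicaid inpatient claims or hospital discharge records. The follow-up for this row is the delivery stay.
3. If the contraception analysis has already been run, mark the delivery-stay row as a post-hoc addition. If the results are published, state under the existing label that it covers insertions up to six weeks after discharge.

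The cost is a table edit, a sentence of definition and a date filter on data already planned for use. The delivery-stay row will have fewer events and so lower precision. The six-week row loses nothing.

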### 3.3. Timing of Study analyses

We will complete this analysis once all study births have occurred, and at least 24 months have elapsed following the last study birth. We will add additional lags to account for the time it takes for administrative records to be complete, sent to the study team, and matched to existing analytic files. Based on the estimated delivery date collected in the baseline survey, the latest expected study delivery date is November 7, 2020. As we define births within a 120-day window of the estimated gestational age as a study index birth, the latest possible date when a study index birth could occur is March 7, 2020. We will allow for twenty-four months of follow-

up from the time of the final possible study index birth (March 7, 2022), six additional months for the study outcomes to be fully incorporated into South Carolina administrative data (September 7, 2023), and an additional three-month buffer for the administrative data to be matched with the study dataset (December 7, 2023). Therefore, we anticipate that analyses of these outcomes will begin in December 2023.

This study includes four birth spacing outcomes. The first three are birth interval indicators defined as having no subsequent live birth observed within 21 (primary outcome), 15 and 24 months (secondary outcomes) of the index birth. The fourth is a continuous outcome defined as the number of months before any subsequent birth within 60 months of the index birth. The analysis for this outcome will include only women who went on to have another birth within 60 months of their index birth. The first three of the birth spacing outcomes described in Table 3.1 will be reported in the main manuscript for the maternal life course objective. The continuous birth interval outcome will be included in a later manuscript which will include longer-term maternal outcomes.

